## 8.1 Statistical analyses for the main objective

### 8.1.1 Estimate Phased RFA 12 month success rate

Success rate estimated as the time to first AF re-occurrence event from the first documented procedure. Data about AF events will be collected since the first documented procedure, including 90 days of the "blanking period" and closes at 12 months FU. If no AF events occur during the follow-up period (considering the "blanking period") up to 12 (+2) months, the case is considered to be "event-free". Calculations will be done for exact 12 months (351 days) after first documented procedure.

Main objective will be calculated for the BAS, FAS and EFAS (see chapter 4 and Appendix B). A successful first documented procedure (successfulness by PVI confirmation) is the basis to calculate the main objective. Patients with a procedure during the "blanking

---

 in the service agreement #2 refers to the final report, which is one and the same document for this study

period" of 90 days after first documented procedure will be excluded from main objective calculations.

Predefined AF re-occurrence definition from CIP Version 2.0 will not be applied to calculate the main objective. Further analysis might be used to estimate Phased RFA success rate considering (re-)occurring left Afl events.

AF re-occurrence event defined as:

- AF pharmacological and/or electrical CV
- AF more the 30 sec on ECG/EGM
- AF less than 30 sec in combination with AF symptoms
- Re-ablations for AF

For this analysis adjudicated AE data and coded AE data (free text fields) will be used. AF re-occurrence event rate will be estimated with and without the use of antiarrhythmic drugs at time of the 12 month follow-up. AF re-occurrence rates will be calculated for patients from BAS and FAS (Appendix B) which need to have a signed 12 month FU / 12 month FU by phone form by definition. AF re-occurrence is defined as the first event of AF re-occurrence event and their related date information based on the following eCRF forms and data fields:

**Table 4:** Main objective variables at 12MFU / General FU form

eCRF field	Related date field	Related FID's annotated eCRF (V1.3, V1.4)
Reason for visit: AF re-occurrence	Date of visit	F11000050 F11000010
Re-ablation reason: Due to AF- occurrence	Date of visit	F11000070 F11000010
History of arrhythmias since last visit: AF	Date of first occur- rence	F12000012 F12000050
History of arrhythmias since last visit: Re- ablation for AF	Date of re-ablation for AF	F12000060 F12000070
CVD hospitalizations during last visit: AF	Date of first admis- sion	F15000020 F15000030

**Table 5:** Main objective variables at 12MFU by phone form

eCRF Field	Related date field	Related FID's annotated eCRF (V1.3, V1.4)
History of arrhythmias since last visit: AF	Date of first occur- rence	F13000010 F12000050
History of arrhythmias since last visit: Re-ablation for AF	Date of re-ablation for AF	F12000060 F12000220
CVD hospitalizations during last visit: AF	Date of first admis- sion	F15000010 F15000020_1 F15000030

**Table 6:** Main objective variables at AE form

eCRF Field	Related date field	Related FID's annotated eCRF (V1.3, V1.4)
Other diagnostics: ~ "AF"	Date of AE	F31000010_88 F30000090 F30000010

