| Individual FU duration | 
Maximum 14 months for each patient
 
The follow up period starts from the date of the first Phased RFA procedure (hereafter „index“) and lasts 12 (+ 2) months.
 
In case the index procedure is unsuccessful (e.g. not all PVIs reached/isolated, procedure prematurely terminated due to patient's clinical status or technical issues), patients will continue their participation in the registry until the end of defined FU period.
 | | | | | | | | |
| Time schedule (tentative) for calendar years | 
 
 Preparation	Q2-Q4 2014	
 
 Recruitment	Q1 2015 – Q2 2018	
 
 Intended last patient out	Q3 2019	
 
 Final Report	Q1 2020	
 
 | Preparation | Q2-Q4 2014 | Recruitment | Q1 2015 – Q2 2018 | Intended last patient out | Q3 2019 | Final Report | Q1 2020 |
| Preparation | Q2-Q4 2014 | | | | | | | | |
| Recruitment | Q1 2015 – Q2 2018 | | | | | | | | |
| Intended last patient out | Q3 2019 | | | | | | | | |
| Final Report | Q1 2020 | | | | | | | | |

1 Introduction

AF is the most common of the sustained arrhythmias affecting millions of people worldwide, with an estimated 2.2 million people in the United States (US) and 4.5 million in the European Union (EU) afflicted with the disorder (1). The overall prevalence of AF is between 2.3% and 2.8% (2). However, the prevalence increases with advancing age, with approximately 10% prevalence of AF in persons aged 70 years or older. The causes of AF are numerous and varied, including ischemic heart disease, post-cardiac surgery, sick sinus syndrome, hypertensive heart disease, idiopathic causes, etc. (3). The prognosis is related to the underlying cause of the disease, with idiopathic causes having the best prognosis and ischemic cardiomyopathy having a poor prognosis (4). AF is associated with an increased incidence of thromboembolic events (stroke and transient ischemia attack), heart failure, and all-cause mortality (5). It is a debilitating disease with symptoms that reduce quality of life and increase the number of hospitalizations. The management of AF is a challenge due to a heterogeneous etiology and tendency for self-propagation of AF, "AF begets AF".

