3.4 Methodology

Patient can sign PIC/PDRF 14 days prior to the scheduled Phased RFA procedure to have sufficient time to consider the participation in the registry.

Observations will be documented at baseline, ablation procedure/hospital discharge and whenever patients visit the medical center with regard to AF recurrence, catheter ablations, Adverse Events, regular medical checkup etc.

Patient will be followed up for minimum 12 and maximum 14 months following first (hereafter "index") Phased RFA procedure. In case the index procedure is performed, but is not successful for medical or technical reasons, patients will stay in the registry until the end of the FU period.

Figure 3-5 provides an overview of the data entry flow chart. The process of data collection is described in Chapter 7. Furthermore, an overview of data to be collected is provided in Table 7-1.

At the baseline visit demographics, medical history, diagnostics, cardiovascular medication and quality of life (QoL) questionnaire ("AFEQT") will be recorded. During the index Phased RFA and all re-do Phased RFA procedures, related variables will be collected including: anticoagulation therapy, general procedure summary, consumables, PV isolation confirmation, adverse events (AE) assessment and hospital discharge status. During the FU period, information about in-hospital visits will be captured in the "General FU" CRFs. The "General FU" CRF contains data about arrhythmia diagnostics, symptoms, hospitalization and cardioversions (from previous visit date to actual visit), re -ablation information, cardiovascular medication, and AE assessment.

At 12 months FU, patients will be either followed up in the medical center ("12 months FU") or by phone ("12 months FU by phone"). Data recorded on the "12 month follow up" CRF is equivalent to the "General FU" CRF, with the addition of the QoL questionnaire (AFEQT). If patient has no reason to visit the medical center between 12 and 13 month after the index procedure, he might be called by study personnel and asked questions for about 15-20 min about any AF symptoms, hospitalizations, AF cardioversions since the previous visit, current medications and quality of life. Whenever 12 months FU performed by phone, data received via CareLink may be used for confirmation of rhythm disturbances. The interview does not replace a medical checkup for the patient and serves as data collection only.

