The "Procedure" CRF will be used to collect data about the ablation procedure and discharge from the medical center. Information regarding anticoagulation therapy, procedure summary information, sedation and consumables, PVI confirmation, cardiovascular medication, date and status at hospital discharge is to be collected. Verification of study defined AEs will be done during the procedure and at the moment of hospital discharge.

If the attempt to conduct Phased RFA ("index" procedure) is not successful for clinical or technical reason, patients will stay enrolled into the registry. If Phased RFA is repeated ("repeated" procedure) or re-do due

to arrhythmia recurrence, the “procedure” CRF should be filled in. Information about all Phased RFA attempts will be used for the analysis. If patient has re-do procedures with some other technology than Phased RFA, Procedure CRF is not required; information about technology which was used for re-ablation to be collected in eCRF “General FU”.

During the Phased RFA, the investigator may require use of other commercially available devices for other ablations such as Afi/LAT or other AF triggers. The use of other devices will be at the investigator’s discretion and use will be documented on the eCRF.

Hospital discharge needs to be completed when the patient is discharged from the hospital, this data to be collected as a part of the procedure visit. Information about date of discharge, reportable adverse event since the procedure and recommended medication information is to be collected. Post-ablation drug regimen is determined at clinical discretion of the treating investigator.

General Follow up visits (in hospital)

The “General” FU CRF will be used to collect data during all standard visits at the site within the following 12 months after the index or study procedure. Data to be collected include: arrhythmia assessment, diagnostics, symptoms, hospitalizations, ablation information and medication. If “General FU” will take place due to system/procedure related AE, “Adverse Event” CRF should be filled in additionally to the “General” FU CRF.

If at any moment during FU, the patient withdraws PIC/PDRF or PI receives information about the patient’s death, the “Exit” CRF should be filled in addition to the “General FU” CRF. All data collected prior to the patient exit will be used for analysis, unless different is required by local laws and regulations.

12 months FU (in hospital or by phone)

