## 4.4 Extended Full Analysis Set

The *Extended Full Analysis Set* (EFAS) consists of all patients of the FAS and thereof patients without documented AF re-ablation (each ablation technology i.e. additional GOLD-AF procedure) until the 12MFU (<351d after the first documented procedure). Also, only patients with a successful first documented procedure (by PVI confirmation) will be member of the EFAS. This population will be used to evaluate the effect of the first documented procedure, in a clearer way.

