## Appendix C: Subgroup analysis

Predefined subgroups (V1.0)

Subgroup description	Analysis set, additional inclusion or exclusion criteria	Tables and scope for analysis
Indication to schedule Phased RFA: Paroxysmal AF	FAS, EFAS incl.: --- excl.: ---	Baseline First documented procedure Additional procedure 12MFU
Indication to schedule Phased RFA: Persistent AF	FAS, EFAS incl.: --- excl.: ---	Baseline First documented procedure Additional procedure 12MFU
Indication to schedule Phased RFA: Longstanding persistent AF	FAS, EFAS incl.: --- excl.: ---	Baseline First documented procedure Additional procedure 12MFU
Successful first documented procedure	FAS, EFAS incl.: --- excl.: ---	Baseline First documented procedure Additional procedure 12MFU
Non-successful first documented procedure	FAS, EFAS incl.: --- excl.: ---	Baseline First documented procedure Additional procedure 12MFU
First documented procedure: PVAC GOLD solely	FAS, EFAS incl.: Phased RFA catheters = PVAC GOLD, general number if catheters used = 1 excl.: adjunctive devices used during the procedure, disregarding sheaths used	First documented procedure Additional procedure GFU 12MFU
First documented procedure: PVAC GOLD + other catheters	FAS, EFAS incl.: Phased RFA catheters = PVAC GOLD, general number if catheters used > 1, additional Phased catheter used (MAAC, MASC and/or Other) excl.: adjunctive devices used during the procedure, disregarding sheaths used	First documented procedure Additional procedure GFU 12MFU
First documented procedure: Phased RFA catheter solely	FAS, EFAS incl.: Phased RFA catheters used, general number if catheters used = 1 excl.: adjunctive devices used during the procedure, disregarding sheaths used	First documented procedure Additional procedure GFU 12MFU
First documented procedure: Phased RFA catheter + adjunctive devices	FAS, EFAS incl.: Phased RFA catheters = PVAC GOLD, general number if catheters used > 1, additional Phased catheter used (MAAC, MASC and/or Other), adjunctive devices used during the procedure excl.: ---	First documented procedure Additional procedure GFU 12MFU
Procedure: Patients with multiple procedures	FAS, EFAS	Baseline First documented procedure Additional procedure

	incl.: patients with > 1 documented procedure excl.: ---	GFU 12MFU

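### SAP 8.1.1 makes the main 12-month success rate conditional on acute procedural success, which conflicts with the protocol's endpoint and with the SAP's own analysis sets

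*SAP*

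**What the plan says.** SAP 8.1.1 assigns the main objective to the BAS, FAS and EFAS. The next sentence reads: "A successful first documented procedure (successfulness by PVI confirmation) is the basis to calculate the main objective". It is not limited to one of the three sets. The section then says that patients who have a procedure during the blanking period "of 90 days after first documented procedure will be excluded from main objective calculations".

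The protocol sets no acute-success condition:
- Section 4.4.1 measures time to first recurrence from the index procedure.
- Section 4.1 includes all enrolled patients in the analysis.
- The synopsis (Individual FU duration) says that after an unsuccessful index procedure "patients will continue their participation in the registry until the end of defined FU period". Section 3.4 says the same: "patients will stay in the registry until the end of the FU period".
- Section 7.2 adds: "Information about all Phased RFA attempts will be used for the analysis".

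Elsewhere the SAP treats acute success differently. The BAS (4.2) needs a started procedure with at least one PV application, and the FAS (4.3) adds a valid 12-month form. Neither requires success. In 4.4, by contrast, "only patients with a successful first documented procedure (by PVI confirmation) will be member of the EFAS". Appendix C lists the subgroup "Non-successful first documented procedure" for both FAS and EFAS, with 12-month follow-up in scope.

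**The concern.** The registry's goal is to describe Phased RFA in routine practice and evaluate its performance, and SAP 2.1 words the main objective for patients scheduled for the procedure. A rate restricted to patients with confirmed isolation answers a narrower question: how patients fare once the procedure has worked acutely. Procedures in which energy was delivered but isolation was not achieved bear directly on system performance, and under 8.1.1 as written they leave the main result. A larger sample does not remove this selection.

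Protocol 4.4 asks that changes to analysis methods be described in the SAP with their justification. SAP 8.1.1 announces its departure from the protocol's recurrence definition, but it neither flags nor explains the success condition.

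**Working it through.** **Passages side by side.**
- If the condition applies to all three sets, the success criterion in the EFAS definition is redundant for the main objective. The EFAS would then differ from the FAS only by its exclusion of AF re-ablations before day 351.
- SAP 8.1.2 plans Cox models of AF re-occurrence for every predefined FAS subgroup with 12-month scope, which includes the failed-procedure subgroup in Appendix C. Under a universal condition that subgroup would have no patients in the main analysis. In the EFAS it is empty by definition.
- SAP 7.2.2 also calls the first documented procedure the basis of the main objective, but without requiring success.
- SAP 8.1.1 excludes patients with a procedure in the blanking period. SAP 8.1.2 treats patients with an additional procedure at any time as not event-free from that procedure on. Both cannot apply to the same patient. Protocol Appendix 1 defines a repeated procedure as a further attempt after an unsuccessful index, so early repeats after a failed index would stay excluded even if the success condition were deleted.

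**The plan's own figure.** The only calculated figure for the main objective is ±3.8% at n = 800, prevalence 20% and design effect 1.2. The formula gives 1.96 × √(1.2 × 0.20 × 0.80 / 800) = ±3.04%, so the stated figure does not reproduce. That is a separate matter, because this figure does not depend on the success condition.

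**Size of the effect.** Let a be the acute success rate, S the 12-month AF-free rate among acute successes, and s the rate among acute failures. The rate over all procedures is aS + (1 − a)s, so the restricted rate is too high by (1 − a)(S − s).

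Inputs from the protocol:
- Acute success: 98% overall (section 1); 98.2% in paroxysmal AF (range 93-100%) and 96.3% in persistent AF (section 4.4.3).
- Chronic success: 74% overall at an average of 10 months; 81.4% paroxysmal and 54.1% persistent at 6 months (section 4.4.1).

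Assumptions, not in the documents: s lies between 0 and 40%, and the cited chronic rates can stand for S at 12 months.

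| Group | Removed per 1000 | s = 0 | s = 40% |
|---|---|---|---|
| Overall (98%, 74%) | 20 | 0.020 × 74 = 1.5 | 0.020 × 34 = 0.7 |
| Paroxysmal (98.2%, 81.4%) | 18 | 0.018 × 81.4 = 1.5 | 0.018 × 41.4 = 0.7 |
| Persistent (96.3%, 54.1%) | 37 | 0.037 × 54.1 = 2.0 | 0.037 × 14.1 = 0.5 |
| Low end (93%, 74%) | 70 | 0.070 × 74 = 5.2 | 0.070 × 34 = 2.4 |

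The last two columns are percentage points. The 93% is quoted for paroxysmal studies; with S = 81.4% the upper bound is 0.070 × 81.4 = 5.7 points. With s = S the difference is zero in every row.

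**Adding the blanking-period exclusion.** Suppose a share b of acute successes has a procedure in the blanking period, all of these count as events, and s = 0. The overall rate is then 0.74 × 0.98 × (1 − b). The documents give no value for b. At b = 1% the rate is 71.8%, or 2.2 points below 74%; at b = 5% it is 68.9%, or 5.1 points below.

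**The case against.** The strongest reply is that the SAP does not settle the matter. The BAS and FAS definitions, 7.2.2, and 8.1.2 with Appendix C all fit an FAS that keeps failed first procedures, and the sentence in 8.1.1 may have been meant for the EFAS alone. That stands. A reader might infer that failed cases certainly never enter the main result, but the documents support only a contradiction. It still has to be resolved, because the sentence is unrestricted as written and two programmers could derive different main rates.

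Other inferences a reader might draw also go too far:
- **The bias must be upward.** This assumes that failed cases do worse, which is plausible but not stated. SAP 8.1.1 also does not say how unverified veins count. SAP 8.3.1 treats a vein that is not isolated or not verified as unsuccessful. If that carries over, some of the patients removed are not treatment failures.
- **Persistent AF is clearly hit harder.** Using 74% for persistent AF would give up to 2.7 points, but the protocol's persistent rate is 54.1%. On that base the paroxysmal and persistent ranges largely overlap.
- **The result will be tested against 74%, or the bias rivals ±3.8%.** The 74% appears as rationale, and the SAP plans no formal comparison with it. The ±3.8% is a whole-cohort half-width for a re-ablation prevalence.
- **Failures are hidden.** SAP 8.3.1.1 reports acute success over attempted procedures, although 8.3.1 drops those without verified confirmation. SAP 8.2.1 analyses safety regardless of procedural success.
- **All failed cases are followed for 12 months.** Under Study Exit in protocol 7.2, sites keep patients who received no energy or did not complete the procedure for 30 days. The synopsis keeps prematurely terminated procedures to the end of follow-up. Those passages need reconciling separately.

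**Conclusion.** The point holds as a conflict between SAP 8.1.1 and both the protocol and the rest of the SAP. Applied as written, the main estimate is success conditional on acute success, which is not the stated objective. At the protocol's average acute success rates the likely effect is modest: 0.7-1.5 points overall and in paroxysmal AF, and 0.5-2.0 in persistent AF. The upper bound is 5.2 points (74% base) to 5.7 points (81.4% base) if acute success is 93%. These figures rest on the assumed 0-40% AF-free rate in failed cases and on reading the cited chronic rates as 12-month rates among acute successes. With equal outcomes the effect is nil. Because the SAP text is contradictory and the registry is descriptive, this is a should-fix point.

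**What to change.** - **SAP 8.1.1, success condition:** delete it for the BAS and FAS. Calculate the main rate there from all first documented Phased RFA procedures with energy delivered, whatever the acute result, with day 0 at that procedure. This fits the existing BAS criterion of at least one PV application.
- **SAP 8.1.1, blanking period:** for the BAS and FAS, remove the exclusion of patients with a procedure in that period, so that the section agrees with 8.1.2, where an additional procedure at any time makes the patient not event-free.
- **EFAS:** keep acute success as a condition here only, and report the result as a labelled secondary estimate. The label should also mention the re-ablation exclusion in SAP 4.4.
- **Appendix C:** run the failed-procedure subgroup in the FAS only.

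The cost is a few SAP sentences, one derivation flag and one Appendix C entry. The procedure outcome and follow-up data are already collected. The downside for the sponsor is a slightly less favourable success rate if failed cases do worse.

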4.3 Sample size considerations

The sample size determination has been based on chronic efficacy, freedom from AF recurrence at 12 months. The sample size calculation is based on the main objective to document real-life mid-term efficacy of patients with atrial fibrillation who have undergone Phased RFA. Efficacy in this case is assumed as the proportion of AF recurrence within 12 months following the index procedure.

The table below shows the sample size needed for estimating a binomial proportion for given prevalence with corresponding precision.

Table 4-1: Table for precision and prevalence for sample size assessment.

| Prevalence | Precision | | | |
|------------|-----------|------|-----|-----|
| | 1% | 2.5% | 5% | 10% |
| 0.1 | 4150 | 665 | 167 | 42 |
| 0.2 | 7377 | 1181 | 296 | 75 |
| 0.3 | 9682 | 1550 | 388 | 98 |

Precision = half-width of a 95% Confidence Interval (CI)

Design effect = 1.2 (variance inflation due to cluster sampling design)

Low sampling rate assumed to have no impact on sample size calculation

Assuming a prevalence of 20% of re-ablations 12 months after treatment, a sample size of 800 will allow the study to estimate the prevalence with a given precision of $\pm 3.8\%$ [range of 95%-CI: 7.6%]. This size guarantees enough information for estimating the prevalence in smaller subgroups (e.g. subgroup with a prevalence of 25% with a precision of $\pm 6.6\%$ [range of 95%-CI: 13.3%]).

A drop-out rate of 25% is assumed, i.e. an estimated drop-out rate of 200 patients. Therefore, it is planned to enroll a total number of patients of approximately 1000.

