4.4 Statistical Methods

All variables collected in the CRF as well as the data obtained from the QoL assessments and all derived parameters will be used in the statistical analysis.

Binary, categorical, and ordinal parameters will be summarized by means of absolute and percentage numbers within the various categories.

Numerical data will be summarized by means of standard statistics (i.e. number of available data, number of missing data, mean, standard deviation, minimum, median, maximum, lower and upper quartile). In addition, adequate graphs (e.g. bar charts, box-whisker plots) may be presented to summarize the results for some parameters.

Time-to-event variables are planned to be analyzed via a Cox proportional hazard regression model presenting hazard ratios and the corresponding 95%-CI. In addition, Kaplan-Meier curves may be presented for these variables. Two-sided 95%-CI will be presented for important parameters, but should be interpreted in an exploratory descriptive way. No formal statistical tests are planned within the statistical analysis.

When all patients enrolled have exited the study, a biometrical report including descriptive statistics of all documented parameters will be generated for the overall patient population as well as for each participating country or region. Patients violating any inclusion criteria will be identified and documented. Depending on the variable(s) of interest, additional selection criteria for subjects (e.g. sub-group analyses) considered in specific analyses may be used, if considered useful during the statistical analysis.

Interim analyses, based on study data reported prior to the final report, may be completed and utilized for publication. No adjustments for alpha are necessary as no hypotheses are being tested.

Any change to the data analysis methods described in the CIP will require an amendment only if it changes main and additional objectives of the CIP. Any other changes to the data analysis methods described in the CIP, and the justification for making the change, will be described in the Statistical Analysis Plan.

The statistical analysis will be performed using SAS (release 9.3 or higher; Cary, NC, USA).

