4.4.1 Statistical methods for the main objective

Estimate Phased RFA 12 months success rate

Rational: Previous studies have demonstrated that Phased RFA with the predicate platinum electrode catheter, PVAC, effectively isolates PVs with an average chronic efficacy of 74% with average follow up of 10 months. The Phased RFA literature meta-analysis published by Andrade, et al (19) reported comparable chronic success (6 months FU) was reported as 81.4% and 54.1% for paroxysmal and persistent AF, respectively.

The clinical effectiveness of PVAC GOLD catheter has yet to be estimated in PMR observational studies to establish if prospective interventional studies outcome is reproducible in daily clinical practice.

Main observational criteria: Success rate estimated as the time to first AF recurrence and/or left Afl and/or AT event from the index procedure. Data about AF events will be collected since the index procedure, including 90 days of the “blanking period” and closes at 12 months FU. If no AF/left Afl and/or events occur during the entire follow up period, 12 (+2) months, the case is considered to be “event-free”.

End point definition:

1. AF pharmacological and/or electrical CV
2. AF and or left Afl more the 30 sec on ECG/EGM
3. AF less than 30 sec in combination with AF symptoms
4. Re-ablations for AF
5. Ablations for left Afl or left AT

Analysis Methods: Freedom from AF recurrence at 12 months will be estimated using Kaplan-Meier methods. A point estimate at the date of 12 months FU post procedure will be presented. Standard error will be approximated using Greenwood's formula, and a two-sided 95% log-log confidence interval will be presented. Day 0 is defined at the date of index procedure. For patients with an AF recurrence, follow up time will be set to the date of recurrence. For patients without a reported AF recurrence, those patients will be censored at the last study contact date.

Limitations: Time to first AF recurrence has practical advantages as a primary endpoint, but does not accurately reflect clinically important parameters such as the frequency, type, and duration of AF recurrence and the overall AF burden. Above known, that significant percentage of patients has silent (or asymptomatic) AF and even more, the tendency to convert symptomatic form AF to asymptomatic after PVI.

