Any change to the data analysis methods described in the CIP will require an amendment only if it changes main and additional objectives of the CIP. Any other changes to the data analysis methods described in the CIP, and the justification for making the change, will be described in the clinical study report.

In order to assess the effects of patients lost to follow-up, percentages of dropouts and reason for loss to follow-up will be summarized. In addition, baseline characteristics of patients who were lost to follow-up in comparison to patients with a complete follow-up will be described.

Additionally, adequate graphs (e.g. bar charts, box-whisker plots) may be presented to summarize the results for some parameters. Further descriptive statistical analyses will be carried out, e.g. correlation analysis (SAP chapter 8.8).

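### The SAP replaces the protocol's main-endpoint list with AF-only events, gives no reason and leaves left atrial flutter optional; separately, it mislabels day 351 as exactly 12 months

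*SAP*

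**What the plan says.** Protocol 4.4.1 sets the main criterion: "Success rate estimated as the time to first AF recurrence and/or left Afl and/or AT event from the index procedure". Its five-item list includes "AF and or left Afl more the 30 sec on ECG/EGM" and "Ablations for left Afl or left AT". The same section then describes the analysis in AF terms only: "Freedom from AF recurrence at 12 months will be estimated using Kaplan-Meier methods". Protocol 4.3 does likewise: "The sample size determination has been based on chronic efficacy, freedom from AF recurrence at 12 months".

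SAP 8.1.1 says: "Predefined AF re-occurrence definition from CIP Version 2.0 will not be applied to calculate the main objective". It substitutes four AF-only events and leaves a left Afl analysis as a possibility. Left AT is not mentioned in SAP 8.1.

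For changes of method that leave the objectives intact, protocol 4.4 says the change "and the justification for making the change, will be described in the Statistical Analysis Plan". SAP chapter 8 repeats the rule with a different destination: "and the justification for making the change, will be described in the clinical study report".

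On timing, SAP 8.1.1 equates 351 days with exactly 12 months, and 8.1.2 and 8.2.2 repeat 351 days as 12 months. Protocol Table 7-2 gives the 12-month visit as day 351 (window start), 365 (target) and 425 (window end).

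**The concern.** This is the registry's main result. A patient whose only arrhythmia after the blanking period is left Afl on ECG/EGM fails under the protocol list and succeeds under the SAP list. The inclusion looks deliberate: the protocol's change table says left AT was added on steering-committee and investigator feedback as the more comprehensive definition. Protocol 4.4.2 and SAP 8.2.1 both name left Afl among arrhythmias arising from ablation, so it bears on a success rate.

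Without a stated reason and a planned companion estimate, a reader of the final report may be unable to judge how much the result depends on the change. Safety reporting does not fill the gap. Protocol chapter 11 collects only procedure- or system-related adverse events, and SAP 7.2.4 analyses only adjudicated ones.

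**Working it through.** **Endpoint lists side by side**

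| Event | Protocol 4.4.1 | SAP 8.1.1 |
|---|---|---|
| Cardioversion for AF | counts | counts |
| AF over 30 s on ECG/EGM | counts | counts |
| Left Afl over 30 s on ECG/EGM | counts | not listed |
| AF under 30 s with symptoms | counts | counts |
| Re-ablation for AF | counts | counts |
| Ablation for left Afl or left AT | counts | not listed |

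Neither SAP 8.1 nor the SAP version history gives a reason.

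**Direction.** Every patient event-free under the six rows is also event-free under the four AF rows. Removing the two left Afl/AT rows, with nothing else changed, can therefore only raise the event-free probability or leave it unchanged. With censoring, the Kaplan-Meier estimate follows this apart from small reweighting when a left Afl/AT event is followed by a later AF event.

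Other SAP rules work the opposite way. Section 8.1.2 treats any additional procedure as a failure. Tables 4 and 5 count AF history and AF hospitalisation, and Table 4 also counts visits for AF; no duration or symptom criterion is shown. The net difference from the protocol list is therefore open.

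**Uneven treatment of ablation.** SAP 8.2.2 lists left Afl as a reason for ablation. A left Afl ablation recorded as an additional Phased RFA procedure is thus a failure under 8.1.2. Protocol 7.2 requires no Procedure CRF for a re-do with another technology, and Tables 4 and 5 list re-ablation only for AF. The same ablation by that route is not shown as counting.

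**Scale of the endpoint change (assumptions only).** Each 1% of all patients with left Afl/AT as the only qualifying event moves the rate by about 1 point. Alternatively, let a fraction q of AF-free patients have such an event, with an AF-only success of 74%. The shift is 0.74 × q:

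- q = 2%: 1.5 points (74% becomes 72.5%)
- q = 5%: 3.7 points (70.3%)
- q = 10%: 7.4 points (66.6%)

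For comparison, the 95% half-width is 1.96 × √(1.2 × p(1−p)/800), using the documents' n = 800 and design effect 1.2:

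- p = 0.814: 2.95 points, about 24 patients
- p = 0.74: 3.33 points, about 27 patients
- p = 0.541: 3.78 points, about 30 patients

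**Day 351.** 351/30.44 = 11.5 months, and 351/30 = 11.7 months. Neither is 12. The day is 14 short of the protocol target of 365.

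For the effect, assume no events before day 90 and S(t) = exp{ln S(365) × ((t−90)/275)^k}. At t = 351 the ratio is 261/275 = 0.949. The protocol's 81.4%, 74% and 54.1% serve only as illustrative day-365 values; it reports them at 6 months, an average of 10 months, and 6 months.

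| S(365) | S(351), k = 1 | Gain | S(351), k = 0.5 | Gain |
|---|---|---|---|---|
| 81.4% | 82.26% | 0.9 | 81.83% | 0.4 |
| 74.0% | 75.14% | 1.1 | 74.58% | 0.6 |
| 54.1% | 55.82% | 1.7 | 54.96% | 0.9 |

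Here k = 1 is a constant hazard and k = 0.5 a falling one; both are assumptions.

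**The case against.** The change is open, and the protocol provides for such changes. SAP 8.1.1 says plainly that it departs and lists what it uses instead. Protocol 4.4 requires an amendment only if the objectives change, and the objective, a 12-month success rate, does not. The protocol's Kaplan-Meier and sample-size sentences already say AF recurrence, so the SAP follows one of two protocol wordings. The registry is descriptive, with no hypothesis or threshold. Tables 4 to 6 show no left Afl/AT follow-up field, so the AF-only list may reflect what was collected.

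Most of this stands, and it limits the point. What it does not supply is the reason, which protocol 4.4 places in the SAP, or a planned estimate showing the effect.

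Four stronger readings are tempting but unsupported:

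- That the reported rate will exceed the protocol-defined rate overall. The offsetting rules above leave the net direction open.
- That the composite must be the main analysis. That depends on the annotated eCRF (SAP Appendix E), which is not in the text available.
- That day 351 hides the later result. SAP Table 13 already plans a Kaplan-Meier analysis to 14 months in the BAS, FAS and EFAS, which runs through day 365.
- That the 81-day last interval in SAP 7.2.3 and the EFAS cut-off in 4.4 are further errors. The interval sorts general follow-up forms and stops where the 12-month window opens. The EFAS cut-off matches day 351 and would conflict only if the read-out moved.

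**Conclusion.** The endpoint point holds and should be fixed. The SAP sets aside the protocol's explicit list for the main objective without the justification that the protocol asks for. It leaves left Afl optional and left AT unaddressed, and it can treat a left Afl/AT ablation differently according to the technology used. That rests on the text and on no model. The isolated effect of the dropped components is towards higher success or none. Its size is unknown, and the figures above are scale only. In a descriptive registry this is a gap in justification and sensitivity analysis, not proof of a biased result.

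The day-351 label is wrong but minor: about 0.4 to 1.7 points under the assumed hazards, below the 3.0 to 3.8 point half-widths.

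**What to change.** **Endpoint, SAP 8.1.1**

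- Give the reason for the AF-only definition, and say how the AF-recurrence wording in protocol 4.3 and 4.4.1 is read against the list.
- Make the CIP Version 2.0 five-item composite a mandatory estimate beside the AF-only one, with the same Kaplan-Meier method and analysis sets, as far as eCRF, adverse-event and coded free-text data allow.
- State which left Afl/AT components cannot be derived. Table 7 has a left Afl adverse-event field. Section 8.3.4 lists left Afl on ECG/EGM, but Table 12 shows no field for it, so the annotated eCRF must be checked.
- Treat ablation for left Afl or left AT the same way whatever the technology.

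The cost is some programming and free-text coding, possibly incomplete capture, and a composite success figure that may be slightly lower.

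**Read-out day**

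Either relabel day 351 in 8.1.1, 8.1.2 and 8.2.2 as the start of the 12-month window and also report the day-365 value from the curve planned in Table 13, or read out at day 365 and align the EFAS cut-off. The first option is mainly wording. The second leaves somewhat fewer patients at risk, because those whose last contact falls on days 351 to 364 are censored before the read-out.
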